4. SUBJECT SELECTION AND WITHDRAWAL CRITERIA

4.1. Number of Subjects:

25 WAS/XLT Patients (10 of whom will have a blood draw only) + 10 Normal Control Patients = 35 Total Patients

4.2. Inclusion Criteria:

In order to be eligible for study entry, subjects must comply with the following:

- Males or females from 3 months to 80 years old
- Signed written informed consent obtained prior to study entry
- Clinical diagnosis of WAS or XLT
- Platelet levels less than $75 \times 10^9/L$
- Adequate renal and hepatic function (creatinine and bilirubin less than or equal to $1.5 \times ULN$, AST and ALT less than or equal to $2.5 \times ULN$)

4.3. Exclusion Criteria:

Any patient is ineligible for study entry if he/she:

- Over the age of 80
- Pregnant or lactating women
- Fertile men who are not practicing or who are unwilling to practice birth control while enrolled in the study or until at least 6 months after treatment

- Aspirin, aspirin-containing compounds, salicylates, non-steroidal anti-inflammatory medications (NSAIDS), clopidogrel or ticlopidine, warfarin or other vitamin K antagonists, unfractionated or low molecular heparin within 7 days of first treatment
- Red blood cell transfusion in the past four weeks
- Elevated ($> 1.5 \times$ ULN) prothrombin time (PT) or partial thromboplastin time (PTT)
- New York Heart Classification III or IV heart disease. Other severe cardiovascular or cardiopulmonary disease, including COPD.
- Known HIV infection, hepatitis B or C infection
- Any infection requiring antibiotic treatment within 3 days
- Other concurrent medical or psychiatric conditions that, in the Investigator's opinion, may be likely to confound study interpretation or prevent completion of study procedures and follow-up examinations.
- Prior malignancy with less than a 5-year disease-free interval, excluding nonmelanoma skin cancers and carcinoma in situ of the cervix

Eligibility criteria for controls:

- a) Within 5 years of the age of the enrolled patient
- b) No overt hematologic diagnosis
- c) Male

4.4. Withdrawal Criteria:

1. Treatment with eltrombopag should be discontinued because of abnormal liver tests if any of the following 4 conditions apply:

- ALT levels ≥ 3 times upper limit of normal (ULN) and bilirubin levels > 1.5 times ($> 35\%$ conjugated bilirubin) ULN,
- (2) ALT levels ≥ 3 times ULN and appearance or worsening of hepatitis symptoms or rash,
- (3) ALT levels remain ≥ 3 times ULN for ≥ 4 weeks, or
- (4) ALT levels are ≥ 5 times ULN.
- If a subject has an adverse experience that would, in the investigator's judgment, make continued participation in the study an unacceptable risk
- Note: If the subject's ALT and bilirubin levels decrease so that both are < 1.5 times ULN, the

investigator may decide to restart the medication and monitor on a weekly basis.

- Study medications will be discontinued in the event of any thrombosis

If subject’s platelet count goes above 200,000, the dose of study medication will be reduced.

As indicated on page 5, perhaps 2-3 of the 15 patients in the study might be at risk over a lifetime for a malignancy such as lymphoma, but it is not very likely to happen during the relatively short time course of the study. If 1 patient develops another type of malignancy or 2 patients develop a Non-Hodgkin Lymphoma during the course of the study, the study will be stopped. Prior to the study being restarted (if this is the desire of the investigators), there will be a formal request to re-open the study submitted to the FDA with a letter of support from Novartis.

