1. INTRODUCTION

1.1. Background

Promacta® (Eltrombopag) received accelerated FDA approval on Nov 20, 2008 for the treatment of thrombocytopenia in patients with chronic immune (idiopathic) thrombocytopenic purpura (ITP) who have had an insufficient response to corticosteroids, immunoglobulins, or splenectomy. Formerly GlaxoSmithKline (GSK) and now Novartis is also developing eltrombopag for the treatment of aplastic anemia, MDS, and chemotherapy-induced thrombocytopenia.

Wiskott Aldrich Syndrome (WAS) is an X-linked disease characterized by immunodeficiency, eczema and thrombocytopenia; a milder form of the disease known as X-Linked Thrombocytopenia (XLT) also exists. The two forms are on a spectrum but typically patients with XLT may be relatively asymptomatic except for signs of bruising and bleeding whereas patients with full blown WAS manifest more symptoms making clinical distinction relatively easy. The estimated incidence in the US is 1 per million people (Sullivan et al. 1994 and Ochs and Rosen 2007). The thrombocytopenia in both WAS and XLT is characterized by: severe thrombocytopenia with platelet counts frequently less than 10-30,000/ul; small platelets which may be dysfunctional; and, as a result, a high rate of serious bleeding including intracranial hemorrhage. Currently patients are treated using platelet transfusion, splenectomy, and/or human stem cell transplantation (HSCT) and experimentally with gene therapy. These are effective in different ways but there appears to be a clearly increased risk of sepsis after splenectomy and morbidity and mortality with HSCT. In addition, even patients with full blown WAS who will undergo transplantation may benefit from waiting until they are 12-24 months of age instead of being transplanted at 2-6 months of age because of relentless thrombocytopenia. There is an estimated 10% risk of malignancy, e.g. development of lymphoma, but this is not usually an early phenomenon. Perhaps 1-3 of the 15 patients in the study might be at risk for lymphoma over a lifetime but it is not likely to happen during the relatively short time course of the study. If it were to happen in one patient, it would be attributed to the natural history of the disease. There would be no specific way to determine the etiology of any lymphoma that developed.

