4.4.1. Study Stopping Rules

1. Two malignancies of any type or 1 malignancy that is not leukemia or lymphoma
2. No platelet increase to > 30,000 in 8 consecutive patients
3. Transaminitis to > 5x ULN in more than 50% of the patients
4. If 33% of patients (with a minimum of 6 patients in the study) achieve the individual withdrawal criteria for liver events, the study will be stopped and reviewed with Novartis and the FDA.

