6.2. Efficacy

Collection of platelet counts on week 1 (pre-dose), week 2, monthly during year 1, every two months during year 2, and every 3 months during years 3-6, along with platelet function studies. Bleeding symptoms will be monitored by bleeding score assessments.

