History of Thromboembolic Events

Thrombotic events can occur at any platelet count. Thrombotic/thromboembolic complications may result from excessive increases in platelet counts. Excessive doses of eltrombopag or medication errors that result in excessive doses of eltrombopag may increase platelet counts to a level that produces thrombotic/thromboembolic complications. In the controlled ITP clinical studies, one thrombotic/thromboembolic complication was reported within the groups that received eltrombopag and none within the placebo groups. Seven patients experienced thrombotic/thromboembolic complications in the ITP extension study.

Caution should be used when administering eltrombopag to patients with known risk factors for thromboembolism (e.g., Factor V Leiden, ATIII deficiency, antiphospholipid syndrome, etc.).

Malignancies and Progression of Malignancies

Stimulation of the TPO receptor on the surface of hematopoietic cells by eltrombopag may increase the risk for hematologic malignancies. In the controlled ITP clinical studies, patients were treated with eltrombopag for a maximum of 6 weeks and during this period no hematologic malignancies were reported. One hematologic malignancy (non-Hodgkin's lymphoma) was reported in the ITP extension study.

Cataracts

Cataracts were observed in toxicology studies of eltrombopag in rodents (see Non-clinical Information). The clinical relevance of this finding continues to be evaluated in all ongoing NOVARTIS sponsored clinical studies. To date, there is however, no evidence that eltrombopag increases the incidence nor progression of cataracts in patients who have received eltrombopag. In the controlled ITP clinical studies, cataracts developed or worsened in five (5%) patients who received 50 mg eltrombopag daily and two (3%) placebo-group patients. In the ITP extension study, cataracts developed or worsened in 4% of patients who underwent ocular examination prior to therapy with eltrombopag. A significant proportion of patients in the ITP clinical studies were also exposed to chronic corticosteroid administration.

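### Section 4.4 stops the study after one leukemia (and, read literally, one Hodgkin lymphoma), while the Study Stopping Rules in 4.4.1 exempt both and omit the FDA step

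*Combined protocol and SAP*

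**What the plan says.** Section 4.4 (Withdrawal Criteria) first remarks that a few of the 15 treated patients may be at lifetime risk of a malignancy, with lymphoma as the only example. It then stops the study "If 1 patient develops another type of malignancy or 2 patients develop a Non-Hodgkin Lymphoma during the course of the study". Before a restart, "there will be a formal request to re-open the study submitted to the FDA with a letter of support from Novartis".

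Section 4.4.1 (Study Stopping Rules), rule 1, gives the trigger as "Two malignancies of any type or 1 malignancy that is not leukemia or lymphoma". It attaches no regulatory step to this rule. Rule 4 of the same list, on liver events, does call for review with Novartis and the FDA.

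On the risk itself, section 6.3 says: "Stimulation of the TPO receptor on the surface of hematopoietic cells by eltrombopag may increase the risk for hematologic malignancies". In the controlled ITP studies, "patients were treated with eltrombopag for a maximum of 6 weeks and during this period no hematologic malignancies were reported". Section 6.3 then reports one non-Hodgkin lymphoma in the ITP extension study. In this trial platelet data are collected "monthly during year 1, every two months during year 2, and every 3 months during years 3-6" (section 6.2).

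A smaller mismatch of the same kind affects the liver rules. Section 4.4.1 rule 4 applies "If 33% of patients (with a minimum of 6 patients in the study) achieve the individual withdrawal criteria for liver events", whereas 6.3.1 activates the 33% rule only once more than six patients are enrolled. The individual discontinuation criteria in 6.3 include progressive ALT elevation. The four liver conditions in 4.4 and 6.3.1 do not.

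**The concern.** A study-level stopping rule should give one answer for each foreseeable event. Here the answer to a single leukemia depends on which section is open. The section whose title marks it as the place to look gives the less cautious answer and leaves out the FDA step.

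The gap falls on a type of event that the protocol itself links to the drug's mechanism. Most treated patients are to be children, and data collection runs to year 6, far longer than the controlled ITP exposure. Section 1.1 explains why one lymphoma would not be alarming: it would be put down to the natural history of the disease. The protocol gives no such reason for leukemia, so nothing shows that the exemption in 4.4.1 was a considered choice. At stake is a delayed or disputed study-level pause, and an FDA step missed by someone who reads only 4.4.1.

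**Working it through.** The plan gives no figure to reproduce here. The check is a comparison of two rules, followed by a rough size for the event.

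**Step 1: the rules side by side.** Section 4.4 names no malignancy other than lymphoma, and its two-case allowance covers Non-Hodgkin lymphoma only. Read literally, any other malignancy is of another type.

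| Event in the study | 4.4 | 4.4.1 rule 1 |
|---|---|---|
| 1 leukemia | stop | no trigger |
| 1 Hodgkin lymphoma | stop (literal reading) | no trigger |
| 1 Non-Hodgkin lymphoma | no trigger | no trigger |
| 1 solid tumor | stop | stop |
| 2 Non-Hodgkin lymphomas | stop | stop |
| 2 leukemias | stop | stop |
| 1 leukemia + 1 Non-Hodgkin lymphoma | stop | stop |

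The rules differ in the first two rows only.

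**Step 2: does another reading remove the difference?** Suppose the other types in 4.4 meant only malignancies outside both leukemia and lymphoma. One leukemia would then trigger neither rule, but two leukemias would stop the study under 4.4.1 and not under 4.4. The mismatch moves; it does not go away.

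**Step 3: does another section settle it?** Section 4.4.2 stops the individual patient for malignancy. Section 6.4.8 lets the DSMB convene if stopping criteria are met, without saying which section defines them. Neither states precedence.

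**Step 4: how likely is a leukemia?** The documents give no leukemia rate.

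Inputs from the documents:
- Malignancy risk R. Section 1.1 says "There is an estimated 10% risk of malignancy", read here as lifetime. Section 4.4 puts 2 to 3 of 15 patients at lifetime risk, or 13% to 20%. The range used is 10% to 20%.
- Follow-up of at most 15 patients x 6 years = 90 patient-years.

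Assumptions:
- The risk is spread evenly over L = 40 to 70 years.
- Leukemia is a share s = 5% to 25% of malignancies.
- The drug has no effect on the risk.

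Formulas: annual rate r = -ln(1 - R)/L; P(at least one leukemia) = 1 - exp(-90 x r x s).

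| R | L (years) | Expected malignancies, 90r | P at s = 5% | P at s = 25% |
|---|---|---|---|---|
| 10% | 70 | 0.135 | 0.7% | 3.3% |
| 10% | 40 | 0.237 | 1.2% | 5.8% |
| 20% | 70 | 0.287 | 1.4% | 6.9% |
| 20% | 40 | 0.502 | 2.5% | 11.8% |

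For the top corner: -ln(0.8)/40 = 0.00558; x 90 = 0.502; x 0.25 = 0.1255; 1 - exp(-0.1255) = 11.8%. The range is about 0.7% to 12%.

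**Step 5: the liver start point.** The smallest count reaching 33% is 2 of 6 (33.3%). At seven patients 2 of 7 is 28.6%, so three are needed, and from there both sections are active with the same counts. They differ only while exactly six patients are enrolled and two or more meet the criteria.

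**Step 6: the liver criteria.** Take ALT rising from 3 to 4 x ULN within four weeks, with normal bilirubin and no symptoms or rash. It is progressive, so 6.3 stops the drug. It meets none of the four liver conditions in 4.4 or 6.3.1. Section 6.1 points to 6.3.1 only.

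**The case against.** The strongest reply is that no two instructions collide. Each section lists conditions sufficient to stop, and 4.4.1 never says that the study continues after one leukemia. A site that obeys every stop instruction would stop and go to the FDA. This stands. A reader might infer that the protocol directs the study to carry on after a leukemia, or that the two sections cannot both be followed; the text supports neither. What remains is an exemption written into 4.4.1 that 4.4 leaves without effect, and a risk that someone relies on 4.4.1 alone.

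Other protections also apply. Malignancy stops the individual patient (4.4.2), cancers are listed as examples of serious events (6.4.2), serious events go to Novartis within 24 hours (6.4.6), and the DSMB reviews semi-annually and may convene for safety concerns (6.4.8). The fault is confined to the study-level rule.

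It would also be tempting to read section 6.3 as evidence that eltrombopag causes leukemia. It is not. The section speaks of hematologic malignancy in general. The one case it reports, in the ITP extension study, is a non-Hodgkin lymphoma, the type on which the two rules agree. The documents report no leukemia on the drug.

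On the liver rules, the start-point difference has no effect once more than six patients are enrolled. The investigator may also stop the drug for unacceptable risk (4.4, 6.3.1), which can cover progressive ALT. These points are minor.

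**Conclusion.** The mismatch is real and should be fixed. As written, 4.4 stops the study at one leukemia and, read literally, at one Hodgkin lymphoma; 4.4.1 exempts both and omits the FDA step. The safe default is to stop, so this is a defect of clarity in a safety rule, not a gap in patient protection. It does not touch sample size or analysis.

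The range of about 0.7% to 12% for leukemia rests on the assumed spans and shares. It is too high if malignancy comes late, as section 1.1 suggests, or if follow-up falls short of six years, for example because effective splenectomy ends participation (5.4.2). It is too low if the drug raises the risk. It does not count Hodgkin lymphoma. The event is unlikely, but the rule exists for such events. The liver differences are secondary. No stopping probability is attached to them, because it would depend on liver outcomes in the patients already enrolled, which the documents do not report.

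**What to change.** State one malignancy rule in 4.4.1 and replace the text in 4.4 with a reference to it:

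- Stop at one malignancy other than Non-Hodgkin lymphoma, or at two malignancies of any type. One leukemia or one Hodgkin lymphoma then stops the study, unless the sponsor, DSMB and FDA expressly exempt Hodgkin lymphoma.
- Carry the FDA re-open request and the Novartis letter of support into the same rule.

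This triggers in the same cases as a literal reading of 4.4, so it loosens nothing.

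In the same amendment, as minor items:

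- State the 33% liver rule once, active from six patients.
- Keep one list of individual liver discontinuation criteria, to which 4.4, 6.1, 6.3 and 6.3.1 all refer. Settle in it whether progressive ALT of at least 3 x ULN stops the drug.

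The cost is amendment wording, plus a slightly higher chance of a precautionary pause than under the 4.4.1 malignancy text or the 6.3.1 liver text.

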4.4.1. Study Stopping Rules

1. Two malignancies of any type or 1 malignancy that is not leukemia or lymphoma
2. No platelet increase to > 30,000 in 8 consecutive patients
3. Transaminitis to > 5x ULN in more than 50% of the patients
4. If 33% of patients (with a minimum of 6 patients in the study) achieve the individual withdrawal criteria for liver events, the study will be stopped and reviewed with Novartis and the FDA.

4.4.2. Patient Stopping Rules

1. Malignancy
2. Transaminase and bilirubin rules
3. Worsening cataracts
4. No increase in the platelet count despite dose increases to > 1.5 mg/kg body weight

5. STUDY TREATMENTS

5.1. Treatment Assignment

1) Review of subject’s medical history
	
2) A routine physical examination, including collection of subject’s height, weight, temperature, blood pressure, and pulse rate, and a review of all medicines
	
3) The study doctor will assess subject’s bruising and bleeding by physical examination and by asking questions. He/she will do this by using the Page ITP Bleeding Score.
 
4) At Screening, about 10-20 mL of blood will be drawn to conduct laboratory tests.
	
5) The starting dose will be based upon weight; patients over 50 kg will start at 50mg daily unless they are of East Asian origin in which case they will use 25 mg as their initial dose. The dose of eltrombopag will be titrated for each subject based on their platelet response. Eltrombopag starting doses for children <50 kg will be scaled by body weight and the starting

--	---	--	---

	that a subject is taking.		dose will be approximately 2mg/kg once daily.
--	---------------------------	--	---

Note: See schedule of events on page 25

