3. INVESTIGATIONAL PLAN

3.1. Study Design

Fifteen patients (approximately 80% children) with WAS/ XLT will be enrolled and undergo baseline screening including not only blood drawing but also history of illness in the past, while ten additional WAS and XLT otherwise ineligible or unwilling patients who will not undergo study treatment and ten control subjects will undergo a one-time blood draw. The pediatric control and non-treatment WAS/XLT subjects will be pediatric patients who are having their blood drawn for reasons not related to an acute illness and will provide a limited amount of additional blood. The pediatric control and non-treatment WAS/XLT subjects will have their blood drawn at Cornell after giving consent. They will not be asked for more than 5-10 ml of blood per year of age up to a maximum of 30 ml total in one draw. Blood drawn will be studied for stem cells and

megakaryocytopoiesis, Immature Platelet Fraction (IPF), and platelet function (see table). These subjects will have their blood drawn for another purpose e.g. pre-op clearance for surgery and therefore it will be a small amount of extra blood posing a minimal risk to the subject. Subsequently, treatment patients will start on 2 mg/kg of eltrombopag and be seen every two weeks in the first month, and monthly for the first year. Although Promacta is commercially available in 25 mg and 50 mg tablets, it is also available for clinical studies in 12.5 mg tablets which will be provided by Novartis for this study. In this study, the starting dose will be based upon weight; patients over 50 kg will start at 50 mg daily unless they are of East Asian origin in which case they will use 25 mg as their initial dose. The dose of eltrombopag will be titrated for each subject based on their platelet response (see table 1). Overall, in this study, doses between 12.5mg every other day and 75mg once daily are anticipated to be required to maintain platelet counts between 50 and 400Gi/L. However, as explained in the provided dosing guidelines, the dose of eltrombopag will be reduced whenever the platelet count exceeds 200Gi/L in order to prevent it from reaching 400Gi/L. The goal is to have a platelet count in a safe hemostatic range, albeit not necessarily a normal platelet count.

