Eltrombopag starting doses for children < 50kg will be scaled by body weight and the starting dose will be approximately 2 mg/kg once daily unless they are of East Asian origin in which case they will use approximately 1 mg/kg as their initial dose. This starting dose is based on the findings of GlaxoSmithKline's PETIT2 study: Eltrombopag for children with chronic immune thrombocytopenia (PETIT2): a randomised, multicentre, placebo-controlled trial.

This dosing schedule is based on those used in GlaxoSmithKline's 'PETIT' study: Eltrombopag in Pediatric patients with Thrombocytopenia from ITP.

For young children unable to swallow a tablet, eltrombopag powder for oral suspension (Eltrombopag PfOS) will be used. Each sachet contains eltrombopag equivalent to 20mg per gm of powder. Please see Appendix 3 for details and dose adjustment guidelines for subjects receiving the suspension formulation. Repeat assessment with the same testing will be performed at week 4. Dose adjustment will be based on the monthly monitoring of the platelet count.

The IPF will be measured at each visit with the CBC. Platelet count data will be collected throughout the study and used as part of the assessment of efficacy. Platelet count data will be collected as part of the CBC monthly during the first year of administration of study drug and at any dose change (eltrombopag or concomitant medication). If a subject continues on a stable dose during any stage of the study for greater than 4 weeks, a CBC (including platelet count) with differential will be performed no less frequently than every 4 weeks. Further information regarding reduction in use of concomitant medications for thrombocytopenia, use of rescue therapy, incidence and severity of bleeding and other symptoms associated with thrombocytopenia and infections will also be collected and summarized.

Platelet function will be assessed by whole blood flow cytometry as described by and in collaboration with [name] (see appendix for attached abstracts).

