10. APPENDICES

1. SCHEDULE OF EVENTS ON THE LAST PAGE OF THE PROTOCOL (PAGE 25).

2. WEEKLY DOSE ADJUSTMENT FOR PLATELET COUNTS:

PLATELET COUNT	DOSE ADJUSTMENT
>200 Gi/L	dose reduced by at least 5%
50 to 200 Gi/L	Maintain current dose
<50 Gi/L and/or Significant Bleeding	Increase daily dose by at least 5% up to 75mg daily

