3.4. Dose Adjustment Guidelines for subjects receiving the suspension formulation

The dose of eltrombopag will be increased or decreased according to platelet counts as outlined above; these modifications will initially be in strength intervals of 30% (rounded up), but intermediate dosing levels may be used if the platelet response warrants it. The dose will be documented in the CRF.

Table 1: Dose Adjustment Guidelines – Suspension formulation

Weight (kg)	Initial dose (mg)	Initial dose (mL)	Adjust dose by (mg)	Adjust dose by (mL) ¹
8	16	8	5	2.5 ¹
9	18	9	6	3 ¹
10	20	10	6	3
11	22	11	7	3.5
12	24	12	8	4
13	26	13	8	4
14	28	14	9	4.5 ¹
15	30	15	9	4.5 ¹
16	32	16	10	5
17	34	17	11	5.5
18	36	18	11	5.5
19	38	19	12	6
20	40	20	12	6
21	42	21	13	6.5
22	44	22	14	7 ¹
23	46	23	14	7 ¹
24	48	24	15	7.5 ¹
25	50	25	15	7.5 ¹

1. For calculated doses of 18mg – 24 mg, patient should receive 20 mg dose (one sachet). For doses of 38 mg to 44 mg, the patient should receive 40 mg dose (two sachets). For doses of 58 mg to 65 mg the patient should receive 60 mg dose (three sachets).

References

Kühne T, Buchanan G, Zimmerman S, Michaels L, Kohan R, et al. A prospective comparative study of 2540 infants and children with newly diagnosed idiopathic thrombocytopenic purpura (ITP) from the intercontinental childhood ITP study group. *The Journal of Pediatrics*, 143, 5:605-608.

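### Section 3.1 halves the starting dose for East Asian children under 50 kg, but section 5.1 and suspension Table 1 give only 2 mg/kg, nominally twice the intended dose

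*Combined protocol and SAP*

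**What the plan says.** The starting dose appears in four places.

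- **Section 3.1, opening statement.** Treatment patients start on 2 mg/kg, with no qualification by weight or origin in that sentence.
- **Section 3.1, weight rules.** Patients over 50 kg start at 50 mg, or 25 mg if of East Asian origin. Children under 50 kg start at about 2 mg/kg "unless they are of East Asian origin in which case they will use approximately 1 mg/kg as their initial dose". For young children who cannot swallow tablets, the section then directs the reader onward: "Please see Appendix 3 for details and dose adjustment guidelines for subjects receiving the suspension formulation".
- **Section 5.1, Treatment Assignment, item 5.** Patients over 50 kg "start at 50mg daily unless they are of East Asian origin in which case they will use 25 mg as their initial dose". For children under 50 kg, the "dose will be approximately 2mg/kg once daily", and the sentence ends without an exception.
- **Appendix 3.4, Table 1.** One initial dose per kilogram of weight from 8 to 25 kg, running from 16 mg to 50 mg. There is no column or footnote for East Asian origin.

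Neither 5.1 nor Appendix 3 refers back to 3.1 for the reduced dose.

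**The concern.** The sponsor chose a halved start for East Asian patients in both weight groups, and that choice is not in dispute. The problem is that it is restated incompletely in places where a starting dose may well be looked up. The omission in 5.1 is selective. One cell keeps the exception above 50 kg and drops it below, so a careful reader could conclude that no reduction applies to smaller children. Table 1 then supplies a ready-made milligram and millilitre figure at 2 mg/kg.

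What is at stake is the first dose given to a young child. Section 3.1 expects about 80% of the 15 treated patients to be children, or about 12 (0.80 × 15), so this is the main dosing group. The documents do not say how many of them might be of East Asian origin; it could be none.

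**Working it through.** **Inputs.** Intended East Asian start: 1 mg/kg (3.1). General start: 2 mg/kg (3.1, 5.1). Suspension strength: 2 mg/mL (Appendix 3.2). First adjustment: 30% of the dose, rounded up (Appendix 3.4). Footnote to Table 1: calculated doses of 18–24 mg become 20 mg, 38–44 mg become 40 mg, and 58–65 mg become 60 mg.

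**Step 1: reproduce Table 1.** Dose = 2 × weight; volume = dose / 2; step = 0.30 × dose, rounded up to a whole mg.

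- 8 kg: 2 × 8 = 16 mg; 16 / 2 = 8 mL; 0.30 × 16 = 4.8, so 5 mg.
- 12 kg: 24 mg; 12 mL; 0.30 × 24 = 7.2, so 8 mg.
- 25 kg: 50 mg; 25 mL; 0.30 × 50 = 15 mg.

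All 18 rows reproduce in this way. The table is intact and is a pure 2 mg/kg schedule.

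**Step 2: nominal ratio.** Listed dose / (1 mg/kg × weight) = 2w / w = 2.0 in all 18 rows. The same nominal ratio follows from 5.1. Below 8 kg and between 25 and 50 kg, where Table 1 has no rows, the point rests on 5.1 alone.

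**Step 3: ratio if the sachet footnote is applied to both starting doses.**

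| Weight (kg) | Listed (mg) | 1 mg/kg (mg) | Listed, rounded (mg) | 1 mg/kg, rounded (mg) | Ratio |
|---|---|---|---|---|---|
| 8 | 16 | 8 | 16 | 8 | 2.00 |
| 9 | 18 | 9 | 20 | 9 | 2.22 |
| 10 | 20 | 10 | 20 | 10 | 2.00 |
| 11 | 22 | 11 | 20 | 11 | 1.82 |
| 12 | 24 | 12 | 20 | 12 | 1.67 |
| 18 | 36 | 18 | 36 | 20 | 1.80 |
| 20 | 40 | 20 | 40 | 20 | 2.00 |
| 23 | 46 | 23 | 46 | 20 | 2.30 |
| 24 | 48 | 24 | 48 | 20 | 2.40 |
| 25 | 50 | 25 | 50 | 25 | 2.00 |

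The rows not shown (13 to 17, 19, 21 and 22 kg) all give 2.00. The range is therefore 1.67 to 2.40, with 2.00 in 12 of 18 rows. Whether the footnote governs starting doses is unclear, because its markers sit in the adjustment column.

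**Step 4: what a corrected table entry would be.** At 1 mg/kg, volume = weight / 2 and step = 0.30 × weight, rounded up.

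- 8 kg: 8 mg, 4 mL, step 3 mg (1.5 mL).
- 20 kg: 20 mg, 10 mL, step 6 mg (3 mL).
- 25 kg: 25 mg, 12.5 mL, step 8 mg (4 mL).
- 24 kg: 24 mg (12 mL) if taken as half the listed dose, but 20 mg (10 mL) if the footnote applies. A correction must settle this.

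**The case against.** The strongest reply is that the rule is already in the protocol. Section 3.1 states the exception and shortly afterwards sends suspension users to Appendix 3, so a reader who follows that pointer has just seen it. No text says that East Asian children should receive 2 mg/kg, and no text names 5.1 or Table 1 as the prescriber's working source. This stands, and it is why the point is conditional on someone dosing from those places alone.

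A second reply concerns harm. A reader might infer that the omission takes a child to a dose the protocol considers unsafe. The documents do not support that:

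- 2 mg/kg is the ordinary paediatric start, and the 16 to 50 mg in Table 1 lie inside the plan's expected range ("doses between 12.5mg every other day and 75mg once daily are anticipated").
- Titration has no ancestry-specific ceiling. Below 50 Gi/L the instruction for everyone is "Increase daily dose by at least 5% up to 75mg daily".
- Patient stopping rule 4 (section 4.4.2) stops treatment for lack of platelet increase only after increases above 1.5 mg/kg, again without exception for origin.

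What is lost is a cautious start. There are no toxicity data by ancestry in the documents.

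A third reply is that treatment starts at one centre and that blood counts, liver tests, dose reduction above 200 Gi/L and the ALT rules limit harm. The single centre lowers the chance of error, although it works from this same protocol. The other safeguards act only after the first dose. Platelet-based titration would not reveal a wrong start: the dose is held at 50 to 200 Gi/L, raised below 50, and lowered only above 200, where the minimum reduction is 5%.

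None of these replies reconciles the texts.

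**Conclusion.** The restatement of the starting dose is incomplete and should be corrected. Followed as written, 5.1 or Table 1 alone gives an East Asian child under 50 kg nominally 2.0 times the dose that 3.1 intends. At 8 to 25 kg the ratio is 1.67 to 2.4 on the assumption that the sachet footnote applies to both starting doses.

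This assumes that staff dose without also applying the exception in 3.1. Someone who applies it makes no error. The clinical consequence, and the number of children it could reach, cannot be quantified from the documents. This is a consistency and safety point only: the choice of dose is not criticised, and no sample-size or analysis figure is affected.

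**What to change.** 1. **Section 5.1.** Extend the sentence on children under 50 kg: *unless of East Asian origin, in which case approximately 1 mg/kg once daily*.
2. **Section 3.1, opening statement.** Mark the 2 mg/kg as subject to the weight and East Asian rules that follow.
3. **Table 1, one added note.** For children of East Asian origin the initial dose is 1 mg/kg (half the listed mg and mL), and the initial adjustment is 30% of that dose, rounded up. The note should also say whether the sachet-rounding footnote applies to this dose, with the 24 kg case as the example (24 mg, or 20 mg if rounded).

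The cost is one clause, one qualifier and one note. No table columns, visits, procedures, sample size or analyses change.
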